1.2.2. Justification for design

This is a prospective observational pilot study. Following 3 groups of participants, including an acute TBI group, a veterans' group with diagnosed TBI and a control group with no previous episodes of brain injury allows us to: (a) assess the changes in fluid and imaging biomarkers and (b) assess mental health status and quality of life over time. Values obtained from levels of biomarkers and measures for mental health status and quality of life will be subtracted from data in the acute TBI and the veteran group. This will reveal changes over time in acute TBI patients who have suffered a TBI and in veterans with TBI. Comparisons between the acute TBI group and the veteran group will then reveal differences between these two groups and whether one group is more susceptible to worse mental health and quality of life status. Since, we will collect longitudinal data, we may be able to tell how long after a TBI do the reported mental health and quality of life problems occur in acute TBI and veterans with a view to developing therapeutic intervention to delay or treat these problems.

We will compare these with the same biomarkers and assessments in control patients (without any episodes of brain injury). This will help us to understand if there is anything different in TBI patients that may tell us who is likely to go onto to develop mental health problems and poorer quality of life outcomes.

Whilst we will aim to perform all investigations at all time points on all patients, not all patients will be able to devote sufficient time and effort to participate and, as this is an exploratory study, we will not exclude patients where they fail to complete all stages of the assessment.

2. Aims, Objectives and Outcome Measures

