2.1. Hypotheses

- 1) TBI alters the structure of the brain causing the development of mental health conditions with time.
- 2) TBI-induced changes can be detected using fluid and imaging biomarkers.
- 3) TBI-induced changes in biomarkers may identify those at risk of poor recovery and the development of mental health conditions affecting the quality of life.
- 4) Changes in visual structure and function predict mental health and quality of life and associate with TBI-related biomarkers.

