12.2. Power Calculation and Statistical Analysis

Data obtained from all clinical examinations and laboratory tests will be compared between the first visit (Contact 1) and the subsequent follow-up visits (Contact 2-6). Many of these data are continuous and normally distributed as well as being repeated measures data of the same subjects. As such, repeated measures ANOVA will be used to determine changes over time. Data that are not normally distributed or numeric will be analysed using non-parametric tests. Linear mixed models, linear regression and analysis of covariance will be used for binary and ordinal outcomes as appropriate. Trial statisticians in the Birmingham Clinical Trials Team will be engaged for further statistical advice, if required.

This is a pilot study to evaluate longitudinal changes in fluid and visual biomarkers of brain injury, mental health status and self-reported quality of life measures in patients with TBI (civilian and military veterans). The sample size is based on:

1) statistical advice that in a pilot / feasibility study, 30 subjects in each group are recommended to allow estimation of the parameters of interest³².

2) Based on Child's et al.³² which showed a difference of 5um in global retinal nerve fibre layer thickness between boxers and controls, an average RNFL thickness of 101. Past experience in the concussion clinic suggests that we are able to follow 80% of patients at the 3-month point (i.e. only 20% lost to follow up). We based the power calculation looking for power to detect a 5um change in the repeated measures, assuming correlation of 0.9 between repeated measures of RNFL thickness (conservative given that in the absence of pathology, RNFL thickness varies very little). Simulated power calculations in R revealed that 24 participants with complete data (recruiting 30 and assuming a 20% drop out) would have >80% power to detect a 2µm change in RNFL thickness and 100% power to detect a 5µm decrease.

13. Ethical Considerations

The study will be performed in accordance with the recommendations guiding physicians in biomedical research involving human subjects, adopted by the 18th World Medical Association General Assembly, Helsinki, Finland, June 1964, amended at the 48th World Medical Association General Assembly, Somerset West, Republic of South Africa, October 1996 (website: http://www.wma.net/en/30publications/10policies/b3/index.html).

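### The analysis fixed in section 12.2 is within-person change from Contact 1, which fits the outcome in 12.1 but neither tests the TBI-induced hypotheses in 2.1 nor delivers the group comparisons promised in 1.2.2

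*Protocol*

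**What the plan says.** Section 12.2 sets one contrast for all clinical and laboratory data: they "will be compared between the first visit (Contact 1) and the subsequent follow-up visits (Contact 2-6". For continuous, normally distributed data, "repeated measures ANOVA will be used to determine changes over time". For the rest, "Data that are not normally distributed or numeric will be analysed using non-parametric tests", and "Linear mixed models, linear regression and analysis of covariance will be used for binary and ordinal outcomes as appropriate". No sentence in 12.2 names a group factor, a group-by-time term or a contrast with controls. Basis 2 of the sample size is also a change in repeated measures, with power quoted for 24 completers.

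Other sections ask for more. Hypothesis 2 in section 2.1 reads "TBI-induced changes can be detected using fluid and imaging biomarkers". Section 1.2.2 promises two group comparisons: "We will compare these with the same biomarkers and assessments in control patients (without any episodes of brain injury", of which it says "This will help us to understand if there is anything different in TBI patients", and "Comparisons between the acute TBI group and the veteran group will then reveal differences between these two groups".

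The schedules in section 6.1 put the acute group's Contact 1 at 0-14 days after head injury or at enrolment, and the veterans' Contact 1 at enrolment. Controls are assessed at enrolment and 6 months only.

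**The concern.** A within-person comparison with Contact 1 has as its null a flat mean over time. The null that matches hypotheses 1 and 2 is that TBI participants have the same levels, and the same change, as people without head injury. The two nulls separate in both directions.

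- A change common to TBI and control participants, such as practice on visual field or saccade tests, rejects the flat-mean null although TBI adds nothing.
- A deficit already present at Contact 1 that then stays constant leaves the flat-mean null true. This is plausible in veterans enrolled long after injury. No group has a pre-injury measurement, so Contact 1 cannot stand in for an uninjured state.

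This is more than detail left for a later plan. Section 12.2 states a contrast, a method and a purpose, and its second sample-size basis rests on the same within-person change. A statistician who followed it as written would leave hypotheses 1 and 2 untested against controls, although baseline and 6-month data are planned in all three groups.

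**Working it through.** **Inputs from section 12.2.** 30 recruited per group, 20% dropout, correlation 0.9 between repeated RNFL measures, power >80% for 2 µm and 100% for 5 µm. **Assumed.** Two-sided alpha 0.05; RNFL SD σ of 5 to 10 µm; for the standardised illustration, SD 1 and correlation 0.5 or 0.7. The protocol gives neither alpha nor an SD.

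**1. The plan's own figure.** 30 × 0.8 = 24 completers, which agrees. For a one-group paired test the SD of change is σ√(2(1 − 0.9)) = 0.447σ, and the noncentrality for a change δ is δ√24 / (0.447σ). Power for 2 µm reaches 80% when σ ≤ 7.49 µm (8.55 µm one-sided), and power for 5 µm is then about 100%. The claim cannot be reproduced uniquely, but it is consistent with a within-person test.

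**2. The same test on the RNFL example, 24 per group, ρ = 0.9, two visits** (40,000 simulated data sets per scenario):

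| True state | Test | σ = 5 | σ = 7.49 | σ = 10 |
|---|---|---|---|---|
| TBI and controls both change 2 µm | within TBI group | 99% | 80% | 56% |
| | group-by-time | 5% | 5% | 5% |
| TBI 5 µm lower at both visits, no change | within TBI group | 5% | 5% | 5% |
| | group-by-time | 5% | 5% | 5% |
| | group difference in mean level | 94% | 64% | 42% |

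The last three rows show that a group-by-time term alone is not enough: it also misses a stable deficit. A level contrast is needed as well. At a single visit, power for a 5 µm difference in level is 92%, 62% and 40%.

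**3. Standardised illustration, 24 per group.** For k contacts with means μ_j, the within-group ANOVA has noncentrality λ = 24 Σ(μ_j − μ̄)² / (1 − ρ).

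- Shared 0.5 SD change, veterans, means (0, 0.5, 0.5): Σ = 0.167, so λ = 8.0 at ρ = 0.5 and 13.3 at ρ = 0.7. Rejection is 69% and 90%.
- Shared 0.5 SD change, acute group, half of it reached at 1 month, means (0, 0.25, 0.5, 0.5): Σ = 0.172, so λ = 8.25 and 13.75. Rejection is 64% and 87%.
- Shared 0.3 SD change: 26-45% in simulation.
- In all of these the difference in 0-to-6-month change between TBI and controls rejects about 5%.
- Stable 0.8 SD deficit: Σ = 0, so λ = 0 and the within-group test rejects 5%. The contrast of mean level over two visits has noncentrality 0.8√12 / √((1 + ρ)/2) = 3.20 (ρ = 0.5) or 3.01 (ρ = 0.7), giving power 88% or 84%.
- TBI flat while controls improve 0.8 SD: within-group 5%. The difference in change has noncentrality 0.8√12 / √(2(1 − ρ)) = 2.77 or 3.58, giving power 77% or 94%.

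**4. What the quoted power becomes for a between-group contrast.** For a 2 µm difference in change, 24 v 24, the noncentrality is 2√12 / (0.447σ) = 3.10, 2.07 and 1.55 at σ = 5, 7.5 and 10. Power is about 86%, 53% and 33%. The standard error is √2 ≈ 1.4 times that of the within-group change. For 80% power about 20, 45 or 79 completers per group are needed, that is 25, 57 or 99 recruited after dividing by 0.8.

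**The case against.** The strongest reply is that this is an unspecified model, not a wrong one. Repeated measures ANOVA can carry a between-subject group factor, model terms are commonly left to a statistical analysis plan, and the within-person contrast matches the outcome in 12.1 and the pilot aim restated in 12.2. The match with 12.1 stands, so the trajectories should stay. What does not follow is that nothing is fixed: 12.2 names the comparison and its purpose, and neither involves a group.

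Several stronger readings are tempting and are not supported.

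- A reader might infer that controls contribute nothing, or that no control comparison is planned. Section 1.2.2 plans one; 12.2 does not turn it into an analysis.
- A reader might infer that the investigators will call any time effect TBI-induced, or take a flat veteran trajectory as no effect. The protocol says neither.
- A reader might infer that the subtraction described in 1.2.2 cannot help. Subtracting one fixed control value would leave the time test unchanged, but visit-matched subtraction is equally open. That would remove a shared mean change from 0 to 6 months. If the sampling error of the control mean were ignored, the test would still reject about 16% under no difference at 24 per group.
- Regression to the mean on the symptom questionnaires should not be invoked, because eligibility does not select on those scores.

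It is also fair that a veteran-control contrast does not isolate TBI. The groups are not randomised, and section 1.2.1 itself notes that combat PTSD and bodily trauma are hard to separate from TBI.

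**Conclusion.** The point holds as a mismatch between sections. The analysis in 12.2 answers whether means move after Contact 1. It does not answer hypotheses 1 and 2 in section 2.1, and it does not deliver the comparisons in 1.2.2. Used alone for those hypotheses, it would flag a shared 0.5 SD change in about 64-90% of studies and a stable 0.8 SD deficit in 5%. On the RNFL example at the protocol's correlation of 0.9, the corresponding figures are 56-99% for a shared 2 µm change and 5% for a lasting 5 µm deficit.

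The sizes are illustrative. They rest on assumed SDs, alpha and effect sizes, and on an assumed correlation for outcomes other than RNFL. The direction does not depend on them: a within-person time test is by construction insensitive to a constant group difference and sensitive to any shared change. The conclusion covers continuous outcomes. Those sent to unnamed non-parametric tests fall under the same Contact 1 comparison, while ordinal and binary outcomes are given other models whose terms are not stated.

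**What to change.** In section 12.2:

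1. Keep the within-group trajectories, including change to 12 months, as estimates with confidence intervals.
2. Add, for each continuous outcome, a linear mixed model over all three groups with group, time and group-by-time.
3. For hypotheses 1 and 2, report the difference from controls in 0-to-6-month change, and the difference from controls in level. For acute TBI give the level difference separately at 0 and 6 months, since averaging would mix the acute phase with recovery. For veterans it may be averaged over both visits.
4. Add the acute-versus-veteran contrast that 1.2.2 promises.
5. State three limits: control-referenced change is available only to 6 months; the groups are not randomised, so differences are associations; and the >80% power for 2 µm belongs to the within-person change, not to the between-group contrast.

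The cost is wording and slightly more analysis work, with no new visits or samples. Between-group intervals will be about 1.4 times wider than within-group ones, so some changes that look clear within a group will not be distinguishable from controls.

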6.1. Summary of assessments

Figure 2. Assessments planned for acute TBI patients

		TRI	AL PERIOD	
	Enrolment	Initial assessment (may be at enrolment)	Post-allocation (monitoring interval clinically determined)	Close-out
TIMEPOINT**	-t1	Contact 1 (0-14 days post head injury or at enrolment)	Contact 2-5 (1, 3, 6 and 9 months after head injury or enrolment)	Contact 6 (12 months after head injury)
ENROLMENT:				
Eligibility screen	Х			
Informed consent	Х			
ASSESSMENTS:				
Collect blood and saliva		X (face to face)	X (1 and 6 months only, face to face)	X (face to face)
Visual function tests (e.g. visual acuity and field tests, optical coherence tomography (OCT), OCT angiography, pupillometry, Email saccadic latency and autorefraction.		X (face to face)	X (1 and 6 months only, face to face)	X (face to face)
Mental health outcomes (social and occupational functioning assessment)		X (face to face and remotely)	X (1 and 6 months only, face to face and remotely)	X (face to face or remotely)
Self-reported measures collected by post (e.g. BIVSS (visual impairment, General anxiety disorder, PTSD, Suicidal behaviour, alcohol use and quality of life		X (all collected remotely)	X (1, 3, 6 and 9 months, all collected remotely)	X (all collected remotely)
Head injury outcome				х

Study name:	Fraumatic brain injury related changes in military veterans					
Protocol version number:	3.0	version date:	11 October 2023	Page:	13 of 22	

		TRI	AL PERIOD	
	Enrolment	Initial assessment (may be at enrolment)	Post-allocation (monitoring interval clinically determined)	Close-out
TIMEPOINT**	- t 1	Contact 1 (at enrolment)	Contact 2-4 (3, 6 and 9 months enrolment)	Contact 5 (12 months after enrolment)
ENROLMENT:				
Eligibility screen	Х			
Informed consent	Х			
ASSESSMENTS:				
Collect blood and saliva		X (face to face)	X (at 6 months only, face to face)	X (face to face)
Visual function tests (e.g. visual acuity and field tests, optical coherence tomography (OCT), OCT angiography, pupillometry, Email saccadic latency and autorefraction.		X (face to face)	X (at 6 months only, face to face)	X (face to face)
Mental health outcomes (social and occupational functioning assessment)		X (face to face and remotely)	X (at 6 months only, face to face or remotely)	X face to face or remotely)

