6.2 Schedule of Assessments and Risks

Screening/enrolment

Study name:	y name: Traumatic brain injury related changes in military veterans						
Protocol version number:	3.0	version date:	11 October 2023	Page:	15 of 22		

Patients' eligibility and willingness to participate will be assessed as described above in the section on consent.

Clinical assessments (Contact 1-6)

All participants recruited will undergo collection of blood and saliva to detect fluid biomarkers of injury, visual function assessments, mental health status and PROMs. Assessments at the 12 month point will be conducted face to face where possible, but where patients are unable to attend (e.g. have moved away) will be conducted remotely. Study time points for visits 2-6 will allow a 10% variation from stated timings. Face to face visits will therefore be at enrolment, 1 month (acute TBI only), 6 months (all patients) and 12 months (acute TBI and veterans where possible).

Taking blood using a needle is uncomfortable, can cause bruising and bleeding and sometimes fainting. Only trained staff will collect the blood samples to ensure this does not occur. Saliva will be collected in a tube and is not invasive and should not cause any problems.

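### The 24 completers per group in section 12.2 rest on a 3-month loss rate, while follow-up OCT runs to 6 or 12 months, so no loss after month 3 is allowed for

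*Protocol*

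**What the plan says.** Section 12.2 gives two bases for the sample size. The first is a general recommendation of 30 per group for a pilot study. The second is a power calculation for retinal nerve fibre layer (RNFL) thickness measured by OCT.

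The second basis takes its loss allowance from a concussion clinic: "we are able to follow 80% of patients at the 3-month point (i.e. only 20% lost to follow up". It then speaks of "24 participants with complete data (recruiting 30 and assuming a 20% drop out", and claims more than 80% power for a 2 µm change and 100% for a 5 µm decrease. The other stated inputs are the correlation ("assuming correlation of 0.9 between repeated measures of RNFL thickness") and the mean ("an average RNFL thickness of 101"). Neither an SD nor an alpha is given.

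The OCT schedule is in section 6. In Figure 3 (veterans) the post-enrolment entry for visual tests, which include OCT, is "X (at 6 months only, face to face", followed by close-out at 12 months. Figure 2 (acute TBI) has 1 month, 6 months and close-out at 12 months. Figure 4 (controls) has 6 months only. Section 6.2 agrees: "Face to face visits will therefore be at enrolment, 1 month (acute TBI only), 6 months (all patients) and 12 months", the last for acute TBI and veterans where possible. The visual-function paragraph of section 6.2, however, places OCT at contacts 1 and 3 and, where possible, contact 6.

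**The concern.** A dropout allowance should refer to the visit at which the powered outcome is measured. Here it refers to month 3. By the figures and the face-to-face list, veterans and controls have their first follow-up OCT at 6 months, and both TBI groups have their last at 12 months. A participant with complete RNFL data must still be attending at 6 or 12 months, so applying the 3-month rate unchanged treats everyone present at month 3 as present at the last scan.

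At stake is the evaluable number that section 12.2 relies on, and with it the basis for the power quoted for the smaller (2 µm) change. The protocol itself expects incomplete follow-up: section 1.2.2 says that not all patients will manage every assessment, and the 12-month scan is only where possible. Section 11 allows the study to end 6 months after the last recruitment, before late recruits reach month 12.

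**Working it through.** **1. Reproduce the plan's number.** 30 × (1 − 0.20) = 24. The arithmetic is exact. The question is which visit the 20% belongs to.

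**2. Set the loss rate beside the OCT visits.**

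| Group | Follow-up OCT by Figures 2–4 | What contact 3 is in that figure |
|---|---|---|
| Acute TBI | 1, 6, 12 months | 3 months |
| Veterans | 6, 12 months | 6 months |
| Controls | 6 months | none (last contact is contact 2) |

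The loss rate is for month 3, and the last scan is at 6 months (controls) or 12 months (both TBI groups). No section gives a loss rate for 6 or 12 months. A count of 24 at the last scan therefore needs zero loss after month 3.

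The paragraph in section 6.2 that puts OCT at contact 3 implies a 3-month scan for acute TBI, against Figure 2 and the visit list in the same section. It does not do so for veterans or controls.

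**3. Evaluable number under assumed total loss.** These rates are assumptions. 30 × 0.7 = 21; 30 × 0.6 = 18; 30 × 0.5 = 15. As a pessimistic bound, if 20% were lost in every 3-month period, 30 × 0.8² = 19.2 would remain at 6 months and 30 × 0.8⁴ = 12.3 at 12 months.

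**4. Power for a 2 µm change.** Paired t-test, noncentral t distribution, two-sided 5% (assumed), r = 0.9 (stated). SD of the difference = SD × √(2(1 − 0.9)) = 0.447 × SD. Noncentrality = (2 / SD of the difference) × √n, with n − 1 degrees of freedom. The SD is not stated, so a range is shown.

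| SD (µm) | n = 24 | n = 21 | n = 18 | n = 15 |
|---|---|---|---|---|
| 5 | 99% | 97% | 95% | 90% |
| 6 | 94% | 90% | 85% | 77% |
| 7 | 85% | 79.5% | 72% | 63% |
| 7.5 | 80% | 74% | 67% | 58% |
| 8 | 75% | 68% | 61% | 52% |
| 10 | 56% | 50% | 43% | 37% |

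The 7.5 row is computed at 7.49 µm, the SD at which n = 24 gives exactly 80%: SD of the difference 3.35 µm, standardised change 2 / 3.35 = 0.597. With a one-sided test that SD would be about 8.5 µm. The protocol's claim of more than 80% at n = 24 can therefore be neither confirmed nor refuted: it holds under this two-sided test for an SD up to about 7.5 µm and fails above that.

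**5. How many further losses matter.** At SD 7.5 µm one loss beyond the planned six gives 78% (n = 23). At SD 7 µm power passes below 80% at n = 21. At SD 6 µm it is still 82% at n = 17. At SD 5 µm it is about 80% even at n = 12.

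**6. Power for a 5 µm change.** For SD up to 10 µm it is 98% or more down to n = 15 (at SD 10 µm: 99.4% at n = 18, 98.0% at n = 15).

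**7. Sensitivity to the test.** Section 12.2 plans repeated measures ANOVA. A simulated overall test across three visits with a steady decline to 2 µm gives lower power than the paired test: at SD 6 µm, 90% at n = 24, 79% at n = 19 and 69% at n = 15. The test behind the quoted power therefore matters as well.

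**The case against.** The case for leaving the text alone has real content. The sample size has an independent basis, 30 per group for a pilot, which this point does not touch. RNFL is not the primary outcome, which section 12.1 defines as change in mental health and quality of life. Section 12.2 frames the calculation around the larger change ("We based the power calculation looking for power to detect a 5um change in the repeated measures"), and power for 5 µm survives heavy loss. Participants with incomplete assessments stay in the study (section 1.2.2), and section 5 foresees methods that cope with missing data. All of this stands and limits the consequence. It does not supply a loss rate for the visits at which RNFL is measured.

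A reader might go further in three ways that the documents do not support.

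- *That no group has OCT at 3 months.* Figures 2–4 and the visit list say so, but the visual-function paragraph of section 6.2, read with Figure 2, puts a scan at month 3 for acute TBI. This is an unresolved contradiction, and neither side can be taken as settled. On either reading, veterans and controls have no 3-month scan, and the acute group also has close-out OCT at 12 months.
- *That the claim of more than 80% power itself assumes no loss after month 3.* Only the count of 24 does. The power figure is a lower bound with no SD or alpha behind it, and could withstand several more losses (SD 6 µm or less) or already fail at n = 24 (SD above about 7.5 µm).
- *That power really is 69% at 6 months or 47% at 12 months*, as 19 and 12 completers would give at SD 7.5 µm. That combines the pessimistic loss bound with the least favourable SD that still fits the claim under a two-sided paired test.

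**Conclusion.** The point holds in limited form. The 24 complete cases per group come from a 3-month loss rate applied to an outcome last measured at 6 months in controls and 12 months in both TBI groups, so they allow for no loss after month 3. That follows from section 12.2 and Figures 2–4 without any assumption.

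The size of the effect does rest on assumptions. With total loss of 30 to 50%, 21 to 15 of 30 remain. Power for 2 µm is then 74 to 58% at SD 7.5 µm and 90 to 77% at SD 6 µm (r = 0.9, two-sided 5%, paired test). It is therefore not shown that power falls below 80%, only that the protocol does not support the number on which it is quoted. The claim for 5 µm is practically unaffected. This is a retention assumption tied to the wrong visit; the multiplication itself is correct.

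**What to change.** In section 12.2:

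- name the OCT visit to which the RNFL power refers;
- replace the 3-month 20% with a retention assumption for that visit and say where it comes from;
- state the SD, the alpha with its sidedness, and the test simulated;
- rerun the simulation and restate the evaluable number and the power for 2 µm at that visit.

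Six months is the one follow-up common to all groups, but the calculation is for change within participants, so choosing that visit is a matter of design.

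Separately, reconcile the contact numbers given for OCT in section 6.2 with Figures 2–4, acute TBI in particular.

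The cost is wording and one rerun. No extra recruitment is needed, provided that a less favourable stated figure is accepted. Holding 24 completers instead would take 24 / 0.7 = 35, 24 / 0.6 = 40 or 24 / 0.5 = 48 recruits per group (rounded up), beyond 30 per group and the overall ceiling of 90, and a pilot does not require that.

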4.1. Inclusion Criteria for acute TBI group

- 1. Over the age of 18
- 2. Must have 2 eyes

3. Not all participants will have capacity to consent (e.g. moderate to severe TBI). For these participants, they will require a personal or nominated consultee.

- 4. Willing and able or consented by consultees to follow the protocol
- 5. Moderate or severe head injury requiring admission to the Queen Elizabeth Hospital within the prior 14 days

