For all participants, a full explanation about the study objectives, visits and assessments will be given in detail and a patient information sheet (PIS) will be provided to facilitate this process. Investigator(s) will also stress that participation is voluntary and that the participant is free to refuse to take part and may withdraw from the study at any time.

In the event that the patient is unconscious, a relative or next of kin will be sought out by the clinical care team to read the Personal Consultee information sheet and personal consultee declaration form (PersCDF). If they are happy for the patient to be involved in the study, they will be asked to sign the consultee declaration form and witnessed by one of the clinical care or research team. If, after including the patient by the PersCDF, the patient's family member thinks the patient would no longer want to be included in the study, they will be withdrawn. For unconscious patients or patients who regain consciousness but do not have the ability to consent, only blood will be collected over time and other measures such as collection of saliva, eye imaging test, SOFAS and PROs will not be possible.

If the patient regains consciousness and is able to consent, the consultee would be notified and the patient would be offered a separate regained capacity PIS and asked if they are happy to be in the study and sign the study consent form. If they would not like to be in the study, the information already collected will be retained and they will be withdrawn from the rest of the study.

Study name:	Traumatic brain inju	Fraumatic brain injury related changes in military veterans					
Protocol version number:	3.0	version date:	11 October 2023	Page:	11 of 22		

If the patient has no relative or next of kin available, a member of the patient's clinical care team will be asked to read the study protocol and PIS and nominated consultee declaration form (ProfCDF). If they are happy for the patient to be involved in the study, they will be asked to sign the nominated consultee declaration form.

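### The 24 complete participants behind the RNFL power allow for 20% dropout but not for acute TBI participants enrolled without capacity, who have no eye imaging

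*Protocol*

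**What the plan says.** Section 12.2 plans 30 participants per group. One basis is a general recommendation for pilot studies. The other is a power simulation for RNFL thickness, which relies on "24 participants with complete data (recruiting 30 and assuming a 20% drop out". The dropout rate comes from a concussion clinic, where "we are able to follow 80% of patients at the 3-month point (i.e. only 20% lost to follow up". The calculation is described as "looking for power to detect a 5um change in the repeated measures", "assuming correlation of 0.9 between repeated measures of RNFL thickness". The result is that the completers "would have >80% power to detect a" 2 µm change, and 100% power for a 5 µm decrease. The same section compares every follow-up visit with Contact 1.

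Section 4.1 enrols moderate or severe head injury into the acute group and states: "Not all participants will have capacity to consent (e.g. moderate to severe TBI". Section 5 adds that for participants who are unconscious, or conscious but unable to consent, only blood is collected and "other measures such as collection of saliva, eye imaging test, SOFAS and PROs will not be possible". The veteran and control groups need capacity to enter (sections 4.2 and 4.3).

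On the 12-month contact, section 6.2 says that assessments "where patients are unable to attend (e.g. have moved away) will be conducted remotely". The same section plans close-out OCT only where possible.

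**The concern.** An acute participant enrolled through a consultee counts as one of the 30 and stays under follow-up, so is not a dropout. If capacity does not return in time for Contact 1, there is no baseline OCT and no RNFL change from Contact 1 to analyse. The 20% does not cover this loss: it is described as loss to follow-up only, and it comes from a concussion clinic, whereas the acute group is moderate or severe injury.

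This is the protocol's only power statement, and it is not separated by group. If the acute group yields fewer complete OCT series than assumed, the stated power does not describe that group. The missing participants are also plausibly the more severely injured, so the RNFL change would be estimated in a milder subset, although the protocol has no figure that sizes this.

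**Working it through.** **Inputs from the protocol.** 30 recruited per group; 20% dropout; correlation 0.9 between repeated RNFL measures; power above 80% for 2 µm and 100% for 5 µm (all section 12.2).

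**Not in the protocol, so assumed.** The share q of acute participants with no Contact 1 OCT; the RNFL SD; alpha and sidedness (taken as two-sided 0.05).

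**Step 1: reproduce the count.** 30 x (1 - 0.20) = 24. It agrees exactly and leaves no margin.

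**Step 2: see what the stated power implies.** For a paired comparison, the SD of change is SD x sqrt(2 x (1 - 0.9)) = 0.447 x SD. With a paired t-test (noncentral t), n = 24 and 2 µm:

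- power of exactly 80% corresponds to an SD of change of 3.349 µm, that is, an RNFL SD of 3.349 / 0.447 = 7.49 µm;
- power of 90% corresponds to an SD of change of 2.894 µm, an RNFL SD of about 6.47 µm;
- an RNFL SD of 5 µm gives an SD of change of 2.236 µm and power of 98.7%.

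The stated power is thus attainable at n = 24 for any RNFL SD up to about 7.49 µm. It cannot be reproduced as a single number.

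**Step 3: expected complete OCT count in the acute group.** n = 30 x (1 - q) x 0.8, with the 20% dropout applied to those who were imaged.

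- q = 0: 24
- q = 10%: 30 x 0.9 x 0.8 = 21.6
- q = 20%: 30 x 0.8 x 0.8 = 19.2
- q = 30%: 30 x 0.7 x 0.8 = 16.8

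To keep 24, dropout among the imaged may be at most 1 - 24 / (30 x (1 - q)). That is 1 - 24/27 = 11.1% at q = 10% and 1 - 24/24 = 0 at q = 20%. Above 20% it is negative, so 24 cannot be reached.

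**Step 4: power for 2 µm at those counts** (n rounded down):

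| q | n | 80% at n = 24 | 90% at n = 24 | RNFL SD 5 µm |
|---|---|---|---|---|
| 0 | 24 | 80% | 90% | 99% |
| 10% | 21 | 74% | 85% | 97% |
| 20% | 19 | 69% | 81% | 96% |
| 30% | 16 | 61% | 73% | 92% |

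Power for 5 µm is above 99% in every cell.

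**The case against.** A reader might infer that the acute group cannot reach 24. The protocol does not show that. It gives no share without capacity. Contact 1 runs from 0 to 14 days after injury or at enrolment, and section 5 lets a participant who regains capacity consent and continue, so entry through a consultee does not by itself mean a missing baseline OCT. At q = 10%, 24 is still reached if dropout among the rest is 11.1% or less. What remains is that capacity regained after Contact 1 comes too late for the baseline, and the 10% timing allowance in section 6.2 covers visits 2 to 6 only.

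A reader might also infer that the power is overstated. That is not demonstrated either. The 69% comes from fixing power at exactly 80% at n = 24, the least favourable reading of a figure printed as above 80%. With an RNFL SD of 5 µm, power is still 80.5% at n = 12.

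The remote 12-month contact is a weaker argument. Section 12.2 does not define complete data as including close-out, section 6.2 already treats close-out OCT as conditional, and remote contacts are open to veterans too. It cannot be counted against the acute group alone.

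On weight: the 5 µm planning effect is unaffected; the pilot recommendation of 30 per group stands apart from the RNFL power; the primary outcome in section 12.1 is mental health and quality of life; and incomplete participants are kept (section 1.2.2). These points limit the importance of the gap but do not close it. The assurance in section 5 about methods for missing data concerns participants who cannot speak and write English, who still have retinal imaging, and it refers to the prediction algorithm. It does not supply the complete data on which section 12.2 is powered.

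**Conclusion.** The point holds as an omitted allowance, not as an arithmetic error. At the stated 20% dropout, expected complete OCT data in the acute group are below 24 for any non-zero q: 21.6, 19.2 and 16.8 at 10%, 20% and 30%. The stated power for 2 µm is therefore unsupported for that group.

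Whether it drops below 80% cannot be decided from the protocol. At q = 20% the answer runs from about 69% to about 96% over the three SD scenarios, and the statement for 5 µm is safe in all of them. These results assume dropout of 20% among those imaged, two-sided alpha of 0.05 and a paired comparison with Contact 1. The veteran and control groups are not affected by this loss, because capacity is an entry criterion for both.

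**What to change.** In section 12.2:

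- Restate the acute group's expected completers as 30 x (1 - q) x 0.8 over a stated range of q, where q is the share with no Contact 1 OCT.
- Re-run the existing simulation at those counts, state the RNFL SD, alpha and sidedness it uses, and report the resulting power for 2 µm.
- Keep 24 for the veteran and control groups only for the comparison of Contact 1 with 6 months.
- Say that 12-month OCT may be less complete in both the acute and veteran groups, because that contact can be remote.

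The cost is some wording and a repeat of a simulation that already exists. No extra patients are needed. The acute group's stated figure becomes less favourable.

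While naming the visits, reconcile the acute schedule: the section 6.2 text places OCT at contacts 1 and 3, whereas Figure 2 makes contact 3 the 3-month contact and lists visual tests between baseline and close-out at 1 and 6 months only.
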